18.2 Serious Adverse Events

Emergency contact details for reporting of serious adverse events are included in the CIP (Appendix A5).

Serious Adverse Events are adverse events that:

- a) led to a death,
- b) led to a serious deterioration in health that either:
 - 1) resulted in a life-threatening illness or injury, or
 - 2) resulted in a permanent impairment of a body structure or a body function, or
 - 3) required in-patient hospitalization or prolongation of existing hospitalization, or
 - 4) resulted in medical or surgical intervention to prevent life threatening illness or injury or permanent impairment to a body structure or a body function.
- c) led to fetal distress, fetal death or a congenital abnormality or birth defect.

In case of a serious adverse event and subsequent need for un-blinding the name-code list can be assessed immediately and breaking the code will not cause any further problem. The data recorded until the report of adverse event will remain included in the dataset.

18.3 Report by the investigator to the sponsor

DMG has implemented and maintains a system to ensure that the reporting of the reportable events will be provided by the investigator to the sponsor in acceptable timely conditions using the Adverse Event/ Adverse Device Effect (AE/ADE) Report Form (Appendix A6).

18.4 Report by the sponsor to the National Competent Authorities

Reportable events will be reported at the same time to all National Competent Authorities where the clinical investigation has commenced.

- a SAE which indicates an imminent risk of death, serious injury, or serious illness and that requires prompt remedial action for other patients/subjects, users or other persons or a new finding to it: immediately, but not later than **2 calendar** days after awareness by sponsor of a new reportable event or of new information in relation with an already reported event.
- any other reportable events or a new finding/update to it: immediately, but not later than **7 calendar** days following the date of awareness by the sponsor of the new reportable event or of new information in relation with an already reported event.

19 Early Termination or Suspension of the Investigation

All materials and devices used in this study have been approved by local regulatory bodies and are currently on the market in various parts of the world. Their clinical use in this investigation is according to label. Therefore, early termination or suspension of the investigation due to problems with the restorative materials is not anticipated.

If the investigation is terminated prematurely or suspended, the principal clinical investigator will promptly inform the clinical investigators of the termination or suspension and the reason(s) for this.

The ethics committees will also be informed promptly and provided with the reason(s) for the termination or suspension by the principal clinical investigator.

If the results of Icon or Control failed or is found to be clinically unsatisfactory, the Principal Investigator will provide an alternative treatment (of a different tooth colored restorative such as a composite resin restorative and bonding system, or other direct restorative system, at the discretion of the clinician,) to the subject. The subject will then be discontinued from the study.

20 Publication Policy

The study investigator may present or publish the results of scientific investigation involving this study. Details are described in the study contract section 6 in detail.

21 Administrative Arrangements

21.5 Projected Time Frame

The clinical study will start as soon as the required ethical approvals have been received and Training has been provided to the clinical team. [REDACTED]

[REDACTED]

The time frame is summarized in table 21.5

Table 21.5 Overview of the study's time frame

time	Study part
[REDACTED]	Study preparation – CIP and IRBs completed
[REDACTED]	Training of clinical team
[REDACTED]	Clinical site preparation
[REDACTED]	Clinical study initiation 
- Patient screening and enrollment- Clinical phase: screening and baseline sessions
[REDACTED]	Baseline report
[REDACTED]	One-year recall
[REDACTED]	One-year report
[REDACTED]	Two-year recall
[REDACTED]	Two-year report
[REDACTED]	Completion of two-year study- Final report

21.6 Financing

Financial agreements regarding funding of the different aspects of the investigation are part of separate contracts between the Sponsor and the Research Team / The Center for Pediatric Dentistry, Seattle, Washington, US.

21.7 Reimbursement to Subjects

Subject compensation and incentives being part of the subject retention package for the clinical site will be part of a separate contract and fall outside the scope of the CIP.

[figure not shown]
21.8 Insurance of the Subjects

[figure not shown]
The study materials in this investigation are cleared by the governing bodies of the participating countries (US, Germany). Therefore, the subjects taking part in the trial are insured by the Sponsor against any injury caused by the study materials under investigation. If applicable, additional regulatory requirements in participating countries will be observed and are part of a separate contract.

[figure not shown]

The primary endpoint in this study is the proportion of study lesions that have progressed, whereby a difference in caries progression of 40% after 2 years between resin infiltrated teeth and control will be assumed. This difference is based on a previous infiltration study by Ekstrand et al. [45] who reported a 1-year difference in caries progression in primary teeth of 39% (resin infiltration (23%) vs. control (62%)), which was furthermore comparable to results obtained in young adults. Martignon et al [42] for example reported a difference in caries progression in permanent teeth of 37% and 38% after 1 and 2 years respectively; and Meyer-Lueckel et al. of 30% after 18 months.

Based on an assumed difference in caries progression of 40% between resin infiltrated teeth and control, with alfa = 0.05 and a power of 80% the calculated sample size (t-test; matched pairs) would be 42 lesions to find significant differences. To allow for a potentially attrition rate of at least 20% over a period of 2 years a total of 50 lesions will be included.

Statistical Analysis

All evaluations are performed by one trained examiner. The primary outcome is proportion of study lesions that progressed after 2 years as measured via dental examination and pairwise comparison of radiographs. Differences between groups will be tested using Fisher's exact test.

Secondary outcomes are the proportion of study lesions that progressed after 1 year as well as change in categorical lesion depth (progression to next depth category lesion; E1->E2->D1->D2->filling) after 1 and 2 years as measured by pairwise comparison of radiographs. In addition, the change in categorical lesion depth will be determined via SFE laser optical device imaging after 1 and 2 years and compared to the change in categorical lesion depth as measured by pairwise comparison of radiographs. Differences in categorical lesion depth will be analyzed with Chi-square tests with 95% confidence interval (95% CI) and P = .05.

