9.3 Randomization

25 non-cavitated early caries lesions will be randomly assigned, using a random numbers table, to study arm 1) the Icon treatment group; and 25 non-cavitated early caries lesions will be randomly assigned, using a random numbers table, to study arm 2) the Control group (OHI and topical fluoridation).

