11.4 Statistical Analysis

11.4.1 Descriptive Statistics

Descriptive statistics (means, standard deviations, counts, and percentages) will be calculated for all variables. A Chi-square test of association will be performed to evaluate if there is a significant difference in caries arrest by treatment group at a significance level of 0.05. Additional Chi-square tests of association will be performed to determine if there is a significant association with the secondary outcomes by treatment group.

11.4.2 **Blinding**

Each subject enrolled into this study will be assigned a unique identifying code number. Every effort will be made to maintain the confidentiality of each study subject's identity. No presentation or publication of the study data will identify any study subject.

11.4.3 **Evaluation of Records**

SFE laser optical device image diagnoses from each time point will be compared to diagnoses from radiograph and visual exams from chart review from the same visit.

- For radiograph and visual exams: Assessments of caries lesions per standard of care will be abstracted from the electronic dental record system (Axium) and recorded on CRF.
- For SFE laser optical device image: Recordings from the device will be used to assess caries lesions and recorded on CRF.

11.4.4 **Missing Data**

Missing data due to dropouts have been accounted for in adjusted sample size. The missing data will be at random. Data of dropouts will be assigned as "last observation carried forward".

11.4.5 **Statistical Software**

STATA Data Analysis and Statistical Software will be utilized to perform data analysis.

12 Method of Reporting

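### The 42-lesion, 80%-power sample size rests on a matched-pairs t-test that fits neither the unpaired 25 + 25 allocation nor the named tests, and 50 lesions less the planned 20% loss leaves 40

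*Combined protocol and SAP*

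**What the plan says.** **Sizing.** The SAP (Sample Size Determination) takes as primary endpoint the proportion of lesions that progress. It assumes a 40-point difference at 2 years, alpha 0.05 and 80% power, and concludes that "the calculated sample size (t-test; matched pairs) would be 42 lesions to find significant differences". The progression rates in the two arms are not given. The support is a study in primary teeth that "reported a 1-year difference in caries progression in primary teeth of 39" points (23% vs 62%). The allowance for loss is an "attrition rate of at least 20% over a period of 2 years a total of 50 lesions will be included".

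**Allocation.** Section 9.3: "25 non-cavitated early caries lesions will be randomly assigned, using a random numbers table, to study arm 1) the Icon treatment group", with another 25 to control. No rule puts one lesion of a pair in each arm. Section 7.2.1 requires one lesion per child and, like section 6.4, allows a second in another quadrant. Section 7.2, however, asks for at least one pair. Sections 8.2, 9.1 and 9.4.2 describe participants being randomised; sections 9.3 and 9.4.1 describe lesions.

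**Test.** SAP (Statistical Analysis): "Differences between groups will be tested using" Fisher's exact test. Section 11.4.1: "A Chi-square test of association will be performed to evaluate if there is a significant difference in caries arrest by treatment group".

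**Dropouts.** Section 11.4.4: "Missing data due to dropouts have been accounted for in adjusted sample size", and "Data of dropouts will be assigned as" last observation carried forward (LOCF).

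**The concern.** A matched-pairs t-test gains its efficiency from within-pair differences. If no pairs are formed, or the analysis ignores them, its sample size says nothing direct about the power of the test that will be run. Here the test is an unpaired comparison of two proportions in 20 to 25 lesions per arm, where Fisher and chi-square themselves differ noticeably.

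The SAP's calculation is the only justification given for the sample size; section 11.2 states a count alone. Hypothesis I (section 4.2.1) is that Icon performs similarly to control. A non-significant result from a test with less power than stated could therefore be misread as support for that hypothesis. The attrition step adds a second problem, because the plan says dropouts are covered when its own figures leave fewer lesions than it requires.

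**Working it through.** **Inputs from the documents.** Difference 40 points, alpha 0.05, power 80%, 42 lesions required, 50 enrolled, loss at least 20%, source rates 23% vs 62% at 1 year (SAP); 25 lesions per arm (section 9.3).

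**Assumptions, not in the documents.** Arm rates 23% vs 63% (the cited 23% plus 40 points), varied below; two-sided test; equal loss in both arms; independent lesions, except in step 4.

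**1. Can 42 be reproduced?** For a paired t-test on a binary outcome, the variance of the within-pair difference is pT(1−pT) + pC(1−pC) − 2ρ√[pT(1−pT)·pC(1−pC)].
- At 23% vs 63%: 0.1771 + 0.2331 − 2ρ(0.2032).
- ρ = 0.1: variance 0.3696, SD 0.608, standardised effect 0.40/0.608 = 0.658. The noncentral t gives 21 pairs, which is 42 lesions.
- ρ = 0: variance 0.4102, standardised effect 0.625, 23 pairs, which is 46 lesions.
- Reading 40% as a standardised effect of 0.40, one-sided, gives 41. That counts pairs, so it means 82 lesions.

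So 42 lesions can be reached near the source rates, but only with real pairs and a small within-pair correlation that the SAP does not state.

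**2. Attrition.**
- 50 × (1 − 0.20) = 40, which is below 42.
- Required for 20% loss: 42/0.80 = 52.5, so 53.
- Loss that 50 can absorb: 1 − 42/50 = 16%.
- 42 × 1.20 = 50.4, so 20% may have been added rather than divided out.

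**3. Power of the named tests.** Power = Σa Σb Bin(a; n, pT) · Bin(b; n, pC) · 1[p-value ≤ 0.05], summed over all outcomes, with n lesions per arm. Entries are Fisher / uncorrected chi-square, in %.

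| Rates (40 points apart) | 25 per arm (no loss) | 21 per arm (42 lesions) | 20 per arm (20% loss) |
|---|---|---|---|
| 30 vs 70 | 78.2 / 85.9 | 62.9 / 74.8 | 59.9 / 71.3 |
| 23 vs 63 | 78.5 / 86.3 | 64.0 / 76.3 | 62.6 / 73.3 |
| 10 vs 50 | 83.3 / 91.1 | 75.9 / 86.1 | 74.2 / 83.8 |
| 5 vs 45 | 90.2 / 95.5 | 84.2 / 91.2 | 81.8 / 89.5 |

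At 20 per arm, Fisher reaches 80% at 5 vs 45 but not at 6 vs 46 (79.9%). Chi-square reaches it at 14 vs 54 (80.3%) but not at 15 vs 55 (79.5%).

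**4. Two lesions per child.** Simulation (200,000 trials per case): 25 lesions per arm, 12 two-lesion children plus one single per arm, both lesions of a child in the same arm, within-child correlation 0.1 to 0.3, tests ignoring the clustering.
- Power at 22% vs 62%: Fisher falls from 78.6% (independent lesions) to between 77.7% and 76.0%; chi-square from 86.4% to between 85.3% and 83.6%.
- Chi-square type I error, 42% in both arms: 6.2% at zero correlation, rising to 7.5–10.1%.
- If each child instead has one lesion in each arm, power at 22% vs 62% rises, to 79.7–82.7% (Fisher) and 87.6–90.8% (chi-square).

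**The case against.** **Pairs may be intended.** Section 7.2 speaks of a pair of lesions. But section 7.2.1 needs only one lesion, section 9.3 has no within-child allocation, and neither document names a paired test between arms. The SAP's pairwise reading of radiographs describes how progression is measured, not matching between arms. Pairing therefore stays an open question, to be settled first.

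**The attrition gap is small, and LOCF may close it.** The gap is two lesions. Section 11.4.4 carries dropouts forward, and section 14.2 repeats this for three causes, though not for lost contact or withdrawal. It also scores some lesions as failures, so those are not lost. This stands: 40 is the SAP's figures worked through, not necessarily the number analysed. But carrying a value forward adds no 2-year information. At 22% vs 62% with 5 lost lesions per arm all carried forward as not progressed, power is 58.5% (Fisher) or 71.9% (chi-square). If the carried value equals the final status, it is 78.6% or 86.4%.

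**Power may be adequate.** This also stands, conditionally. Low infiltrated rates restore 80%, and one cited source reports 4% vs 42% at 3 years.

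**A stronger reading to avoid.** A reader might infer that the trial is shown to be underpowered and must enrol more lesions. The documents do not support that. They give no arm rates, chi-square at 25 per arm exceeds 80% at every rate pair in the table, and the analysed number depends on how LOCF is applied.

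**Conclusion.** The point holds, and two parts need no assumption: the sizing method matches neither the allocation text nor either named test, and 50 lesions less 20% is 40, short of the SAP's own 42. The statement in section 11.4.4 that dropouts are accounted for is therefore not met on the SAP's figures.

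The power consequence is conditional on arm rates, a two-sided 0.05 test, equal arms and independent lesions. At 23% vs 63%, the 42 lesions said to give 80% give 64.0% (Fisher) or 76.3% (chi-square). The method mismatch carries the weight; the two-lesion gap is minor. This must be corrected, because the 80% figure is the trial's only stated justification for its size.

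**What to change.** 1. **Settle the design first.** Reconcile section 7.2 with sections 7.2.1 and 9.3 on pairing. Reconcile the unit of randomisation: participant in sections 8.2, 9.1 and 9.4.2, lesion in sections 9.3 and 9.4.1. State no power figure until this is done.
2. **If unpaired.** Delete the matched-pairs method and the 42-lesion and 80% figures that depend on it. Name one primary test in both the SAP and section 11.4.1. Give its power with and without the planned loss, with arm rates labelled as assumptions. For example, at 23% vs 63%, two-sided 0.05, independent lesions: Fisher 78.5% at 25 per arm and 62.6% at 20 per arm; or uncorrected chi-square 86.3% and 73.3%. Add the range at 20 per arm for the same 40-point difference (30 vs 70 to 5 vs 45): Fisher 59.9% to 81.8%, chi-square 71.3% to 89.5%. Replace the attrition sentence with a statement that 50 lesions less 20% leaves 40 evaluable, with the matching power, and align section 11.4.4.
3. **If paired.** Keep the paired sizing, name a paired test, and say that 50 lesions allow 16% loss from 42.
4. **Either way.** State what is assumed about within-child correlation. The example figures in item 2 assume independent lesions. With up to two lesions per child, placing both in one arm lowers power and can raise the error rate of a test that ignores clustering.

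**Cost.** Wording only, with no extra lesions, if unpaired; the stated power becomes less favourable and visibly depends on assumptions. If pairs are intended, the eligibility text, the allocation text and the named tests must also change.

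### Change in lesion depth is defined on an ordered scale but tested with an unordered Chi-square at 20 to 25 lesions per arm, which gives up power that a rank test would keep

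*Combined protocol and SAP*

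**What the plan says.** The SAP (Statistical Analysis) names as a secondary outcome the "change in categorical lesion depth (progression to next depth category lesion; E1->E2->D1->D2->filling) after 1 and 2 years", read from paired radiographs. The test follows: "Differences in categorical lesion depth will be analyzed with Chi-square tests with 95% confidence interval (95% CI) and P = .05". Protocol 11.4.1 does the same for the protocol's own secondary endpoints: "Additional Chi-square tests of association will be performed to determine if there is a significant association with the secondary outcomes by treatment group". Neither place names a rank, trend, ordinal-model or exact method for these outcomes. Fisher's exact test appears in the SAP for the primary outcome only.

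On numbers, protocol 9.3 assigns 25 lesions to each arm, and the SAP (Sample Size Determination) states: "To allow for a potentially attrition rate of at least 20% over a period of 2 years a total of 50 lesions will be included". Baseline lesions are E1 or E2 only (7.2.1).

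Two sections bear on which depth categories can be seen at follow-up. Protocol 9.5 ends participation when a lesion moves from E2 into a D category. Table 14.1.2 in section 14.2 has a lesion treated and scored as a failure when it reaches D2 or D3.

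**The concern.** Pearson's Chi-square gives the same p-value if the depth categories are shuffled. In a table of two arms by k categories it spreads its sensitivity over k - 1 degrees of freedom. A treatment that slows progression should move lesions in one direction along the scale, and a rank or trend test aims one degree of freedom at that pattern. At 20 to 25 lesions per arm the difference can decide whether a real shift in depth is detected.

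The table is also sparse. The SAP gives the primary 2x2 table an exact test, but gives the sparser depth table none.

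This point concerns the comparison between arms. The comparison of SFE with radiographic readings is a separate question.

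**Working it through.** **1. The plan's own figure.** The SAP says "the calculated sample size (t-test; matched pairs) would be 42 lesions to find significant differences". With 63% versus 23% progressed (the assumed 40-point difference), two-sided alpha 0.05 (sidedness is not stated) and 80% power, the unpooled normal formula gives

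n = (1.960 + 0.842)² × [0.63×0.37 + 0.23×0.77] / 0.40² = 7.849 × 0.4102 / 0.16 = 20.1, so 21 per arm and 42 lesions.

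The figure of 42 reproduces, though the SAP gives no SD or within-pair correlation for its matched-pairs label. It concerns the primary outcome. No power is stated for depth change.

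**2. Lesions available.** 50 × (1 - 0.20) = 40, or 20 per arm after the stated attrition, and 25 per arm with none.

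**3. Expected counts.** The documents give no category distribution, so one is assumed: 0/1/2/3 steps at 38/36/17/9% on control and 77/14/6/3% on Icon. This keeps the cited 62% and 23% progressed. The arm averages are 57.5/25/11.5/6%. At 20 per arm the expected counts are 11.5/5.0/2.3/1.2, and at 25 per arm 14.4/6.2/2.9/1.5. Over the assumed sets, about 45% to 78% of cells have an expected count below 5 with four or five categories, and 27% to 43% with three.

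**4. Power.** Multinomial simulation, 20,000 to 60,000 trials per row, lesions treated as independent, two-sided 0.05. Each power pair is Chi-square versus Wilcoxon rank-sum, in per cent. PO means a proportional-odds shift to the stated percentage progressed on Icon.

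| Steps, control % | Icon % | 20 per arm | Loss | 25 per arm | Loss |
|---|---|---|---|---|---|
| 38/62 | 77/23 | 71.2 v 71.2 | 0 | 84.5 v 84.5 | 0 |
| 38/50/12 | 77/19/4 | 61.7 v 70.8 | 9.1 | 72.7 v 80.4 | 7.7 |
| 38/37/25 | 77/14/9 | 62.3 v 70.1 | 7.8 | 72.3 v 79.2 | 6.9 |
| 38/36/17/9 | 77/14/6/3 | 53.8 v 70.1 | 16.3 | 65.3 v 79.6 | 14.3 |
| 38/25/22/15 | 77/10/8/5 | 53.5 v 69.8 | 16.3 | 65.5 v 79.5 | 14.0 |
| 38/34/18/10 | PO to 24% | 52 v 73 | 21 | 64 v 82 | 18 |
| 38/34/18/10 | PO to 30% | 37 v 57 | 20 | 47 v 67 | 20 |
| 38/34/18/10 | PO to 35% | 26 v 43 | 17 | 34 v 52 | 18 |
| 38/33/16/9/4 | 77/12/6/3/2 | 49.2 v 68.4 | 19.2 | 60.8 v 77.8 | 17.0 |
| 38/22/17/13/10 | 77/9/6/5/3 | 46.9 v 70.1 | 23.2 | 59.0 v 79.5 | 20.5 |
| 38/30/17/10/5 | PO to 23% | 48.5 v 75.3 | 26.8 | 61.2 v 84.5 | 23.3 |

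Collapsing the 38/34/18/10 set to three categories gives losses of about 9 to 12 points. A linear-trend test with equally spaced scores gains less than the rank test: about 3 to 22 points over Chi-square in the sets with three or more categories.

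**5. Error rate.** With the same distribution in both arms, Chi-square rejected 4.3% to 5.2% of the time in the three- and four-category sets and 3.1% to 3.8% in the sparser five-category sets. The rank test held about 5%.

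**6. Binary secondary outcomes.** An expected event count falls below 5 when the average event rate is under 5/20 = 25% at 20 per arm, or under 5/25 = 20% at 25 per arm. At assumed average rates of 5% to 12.5% the expected count is 0.05 × 20 = 1.0 to 0.125 × 25 = 3.1 per arm. The documents state no rates.

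**The case against.** Five arguments run against the point.

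- *The number of categories is not settled.* If 9.5 governs, an E2 lesion normally shows at most one step and an E1 lesion about two. The three-category rows then apply, with a loss of 7 to 12 points. If Table 14.1.2 governs, deeper categories can occur. This stands: no single loss figure can be given. A reader might take the 16 to 19 points that some four-category sets produce as a property of the plan, but that figure depends on an assumed distribution.

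- *The outcome may be yes/no.* The SAP's gloss about moving to the next category could be read that way, and then nothing is lost. This reading is weak. The proportion progressed at 1 year is listed beside depth change, and the proportion at 2 years is the primary outcome, so a binary version would largely repeat both.

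- *Small expected counts do not make the p-value wrong.* A reader might infer that sparse cells produce false positives. The null simulations do not show this: the test is close to nominal or mildly conservative.

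- *Depth change may add little to the binary result.* In the proportional-odds set at 25 per arm, rank-sum power is 82/67/53%, against 83/67/54% for a plain Chi-square on progressed yes/no. This stands as a limit on what the fix buys: it restores what the unordered test loses, but does not make depth change clearly stronger than a yes/no comparison.

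- *Rare secondary events are not documented.* A reader might infer that sensitivity and secondary caries are rare. No rates are given, so this remains an assumption.

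**Conclusion.** The mismatch is in the text: an ordered outcome, an unordered test, and no ordinal or exact alternative. The cost is power: about 7 to 12 points with three change categories, about 14 to 21 with four, up to about 27 with five, and none if the outcome is binary. These figures assume 62% progressed on control and 23% to 35% on Icon, invented splits over the deeper categories, 20 to 25 lesions per arm, and independent lesions, although up to two per child are allowed. Inflated false positives are not shown. In every set examined the rank test had at least the power of Chi-square. Because the outcome is secondary and the SAP's primary test is untouched, this is a worthwhile, cheap improvement and not a threat to the main result.

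**What to change.** In the SAP and in 11.4.1:

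1. Test depth change between arms with a Wilcoxon rank-sum test (or a linear-by-linear trend test, with its scores stated), stratified by baseline E1/E2, with a permutation p-value.
2. Make the permutation follow the randomisation and keep a child's two lesions together as they were randomised. Section 9.3 assigns lesions while 8.2 and 9.1 speak of participants, so the unit must be stated.
3. Define the categories. Say how filling is ranked: it is four steps from E1 and three from E2, and section 14.2 sends lesions treated by an external dentist to last observation carried forward. Say also where D3 belongs, since it is in Table 8.4.2.2 but not in the SAP's chain.
4. Reconcile 9.5 and Table 14.1.2 on when a lesion leaves the study, because this sets which categories can be observed.
5. For binary secondary outcomes with small expected counts, use Fisher's exact test, as the SAP does for the primary outcome. This adds consistency and error control, not power.
6. Keep the table of percentages by arm, and report a common odds ratio with its 95% confidence interval.

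The cost is wording, plus the decisions in items 2 to 4. No extra children, visits or data are needed. The downside is that the summary becomes a shift or common odds ratio, which is less direct than percentages; the table in item 6 covers that.

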6.2 Specific Aimes (Primary Endpoints)

6.2.1 Specific Aim I

- Caries arrest evaluated by bitewing radiographs

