6.2.2 Specific Aim II

- Confirm optical measurements from SFE laser device correlate with clinical measures

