6.3 Secondary Endpoints

- White spot reversal
- Secondary caries
- Post-operative sensitivity
- Color match / surface staining
- Surface quality / texture
- SFE for visualization of early caries and lesion depth assessment

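### No stated analysis can show whether SFE readings track radiographic depth: Chi-square is the only test the SAP names for categorical depth, and its table layout is not given

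*Combined protocol and SAP*

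**What the plan says.** Protocol 6.2.2 states the device aim: "Confirm optical measurements from SFE laser device correlate with clinical measures". Section 6.3 adds, among the secondary endpoints, "SFE for visualization of early caries and lesion depth assessment".

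Protocol 11.4.3 says that "SFE laser optical device image diagnoses from each time point will be compared to diagnoses from radiograph and visual exams from chart review" at the same visit. It names no statistic for this. The Chi-square tests in 11.4.1 are by treatment group.

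The SAP (Statistical Analysis) says that "the change in categorical lesion depth will be determined via SFE laser optical device imaging after 1 and 2 years". It sets this SFE result against the radiographic change for the same lesions. Its next sentence is "Differences in categorical lesion depth will be analyzed with Chi-square tests with 95% confidence interval (95% CI) and P = .05". The only other test in the SAP is for the primary outcome: "Differences between groups will be tested using Fisher's exact test".

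Neither document mentions kappa, a correlation coefficient, a paired test, sensitivity or specificity, or a level of correlation or agreement that would count as confirming the device aim.

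**The concern.** SFE and radiograph give two readings of the same lesion on an ordered scale. Whether one tracks the other calls for a paired, ordinal summary that has a size and a direction. A nominal Chi-square supplies neither, whichever way the table is set up.

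The device conclusion is at stake. A non-significant result from a table of methods by category could be taken as evidence that the methods match when they agree only by chance. A significant result from a cross-table could be taken as confirmation when the readings run in opposite directions. The SAP sentence mentions a 95% confidence interval but does not say for what quantity, so it does not fill the gap.

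**Working it through.** The documents give no sample size, target or expected value for the SFE comparison, so there is no figure of theirs to reproduce. The check is whether Chi-square, in either layout, can separate good readings from bad ones.

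**Inputs from the documents.** The SAP plans 50 lesions and allows for attrition of at least 20%, so at most about 50 × 0.8 = 40 lesions have paired readings at two years. Up to two lesions per child are allowed (protocol 6.4).

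**Assumptions.** The cell counts below are illustrative. Depth change is reduced to progressed yes/no, and clustering within children is ignored.

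**Notation.** Rows are radiograph progressed/not and columns are SFE progressed/not, with cells a, b; c, d and n = 40.

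- Methods stacked as two groups of 40: X² = 2n(b − c)² / [(2a + b + c)(2d + b + c)]. This is zero whenever b = c, however many lesions are read differently.
- Cross-table: X² = n(ad − bc)² / [(a+b)(c+d)(a+c)(b+d)]. The square removes the direction.
- Kappa = (pₒ − pₑ)/(1 − pₑ), with pₒ = (a + d)/n and pₑ = [(a+b)(a+c) + (c+d)(b+d)]/n².

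| Assumed table (a, b; c, d) | Raw agreement | Kappa | Stacked X², p | Cross-table X², p |
|---|---|---|---|---|
| Perfect: 17, 0; 0, 23 | 100% | 1.00 | 0.00, 1.00 | 40.0, 2.5e-10 |
| Chance-level: 7, 10; 10, 13 | 50% | −0.02 | 0.00, 1.00 | 0.02, 0.88 |
| Mostly opposite: 3, 14; 14, 9 | 30% | −0.43 | 0.00, 1.00 | 7.47, 0.006 |
| Total reversal: 0, 20; 20, 0 | 0% | −1.00 | 0.00, 1.00 | 40.0, 2.5e-10 |
| One-way shift: 17, 0; 8, 15 | 80% | 0.61 | 3.21, 0.073 | 17.7, 2.5e-5 |

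Worked examples:

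- Mostly opposite, kappa: pₒ = 12/40 = 0.30 and pₑ = (17² + 23²)/1600 = 0.511, so kappa = −0.211/0.489 = −0.43.
- Mostly opposite, cross-table: 40 × (27 − 196)² / (17 × 23 × 17 × 23) = 7.47.
- One-way shift, stacked: 80 × 64 / (42 × 38) = 3.21. The exact McNemar test on the 8 discordant lesions, all in one direction, gives 2 × 0.5⁸ = 0.008.

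**Stacked layout.** It cannot tell the first four rows apart, and in the fifth it misses at the 5% level a shift that the paired test detects.

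**Cross-table layout.** It keeps the pairing and does separate chance from perfect agreement, but it cannot tell perfect agreement from total reversal.

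**More than two categories.** The same limits hold. The stacked statistic depends only on the two sets of marginal totals. The cross-table statistic is unchanged if the SFE categories are put in any other order, so it cannot use the E1, E2, D1, D2 ordering.

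**What a paired summary would give.** With 14, 3; 3, 20, raw agreement is 85% and kappa is 0.69, with a large-sample 95% CI of 0.47 to 0.92 before any allowance for clustering.

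**The case against.** Four stronger readings are tempting, and the documents do not support them.

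- *That the SAP prescribes a test which ignores the pairing.* This is certain only for a stacked table, and the layout is not stated. The Chi-square sentence may even have been meant for treatment arms, since protocol 11.4.1 uses Chi-square for secondary outcomes by group. In that case the fault is an omission: the SFE comparison has no method at all.
- *That Aim II is about agreement.* Its wording is correlation, and Hypothesis II says only that progression may be imaged. An SFE that reads consistently one grade too deep could still satisfy Aim II, so a significant association there would not be a false conclusion. What stands is narrower: Chi-square gives no strength or direction, so opposite readings would pass as well. Agreement matters for the separate claim in 6.3 and the SAP that SFE assesses depth on the radiographic categories.
- *That a primary endpoint is left unanalysable.* The heading of 6.2 calls the aims primary, but 6.1 calls SFE a secondary purpose, 6.3 lists SFE depth assessment as secondary, and the SAP introduces it as an addition. The documents conflict, and this point does not depend on which is right.
- *That the baseline images should carry the main analysis.* Enrolled lesions are radiographically E1 or E2 only (7.2.1), so the range is restricted. Baseline also contains no progression, so it cannot answer the SAP's comparison of change.

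Two further limits stand. Protocol 4.1 regards radiography as an imperfect measure of early caries, so agreement with it is not proof of accuracy. The SAP has one examiner perform all evaluations, so any agreement measure would be inflated if the readings are not made independently.

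**Conclusion.** The concern holds in this form: the only test that the SAP could apply to SFE against radiograph is Chi-square, and in neither layout does it show that the readings correlate in the right direction or agree on depth. If the sentence does not cover the SFE comparison, nothing does.

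The size is shown by illustration, because the documents give no expected SFE results. In 40-lesion tables with assumed counts, the stacked test returns p = 1.0 for kappa of 1.00, −0.02, −0.43 and −1.00, and the cross-table test returns 40.0 for both kappa 1.00 and kappa −1.00. The algebra behind these results does not depend on the counts chosen.

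The plan should be corrected on this point. The conclusion concerns the device aim only; the comparison of infiltration with control is not affected.

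**What to change.** Amend the SAP as follows.

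1. Restrict the Chi-square sentence to between-arm comparisons.
2. Cross-tabulate SFE against radiograph lesion by lesion, for depth category at each visit and for change at 1 and 2 years.
3. Report an ordinal correlation, which answers Aim II as worded, together with weighted kappa and raw agreement for SFE against radiograph. Take 95% CIs from a bootstrap that resamples children, because a child may contribute two lesions.
4. Add a paired test of marginal shift: McNemar for progressed yes/no, Bowker or Stuart-Maxwell for depth categories.
5. Cover the visual exam, which 11.4.3 names and the SAP omits. Its scale (Table 8.4.2.1) differs from the radiographic one, so compare it by progressed/not progressed or by rank.
6. Report baseline and follow-up separately. At baseline, give raw agreement beside kappa because the radiographic range is E1 to E2. Split follow-up by arm, because protocol 4.1 says infiltration changes how a lesion looks.
7. State in advance what level of correlation or agreement would confirm the device aim, and whether SFE images are read without sight of the radiographic result.

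The cost is SAP wording and a little more analysis. The readings are already scheduled (protocol 9.5), so no new data are needed. With about 40 to 50 lesions the intervals will be wide, and the report should say so.
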